## **SECTION 9: CONTRACEPTIVE & CONDOM USE SELF-EFFICACY (Other variables)**

We are now going to ask you some questions about what is important to you when selecting a birth control method to use when you have sex.

9.1 Indicate how important or unimportant these things about birth control are to you when selecting a birth control method to use to prevent pregnancy. Use this scale for your answers:

1. Not important
2. Slightly important
3. Moderately important
4. Very important
5. Extremely important

a. Does not require me to touch my partners genitals

1    2    3    4    5

b. Is not messy to use.

1    2    3    4    5

c. Does not have to be washed or stored.

1    2    3    4    5

d. Can be bought without seeing a health care provider or getting a prescription

1    2    3    4    5

e. Can be used without your knowing about it.

1    2    3    4    5

f. Only needs to be used when I have sex.

1    2    3    4    5

g. Reduces your chances of getting HIV.

1    2    3    4    5

h. Reduces your chances of getting an STD other than HIV.

1    2    3    4    5

i. Does not cause side effects like bleeding, cramps, weight gain, or changes in mood in [NAME].

1    2    3    4    5

j. Does not cause pain or irritation.

1    2    3    4    5

k. Will not decrease sexual pleasure for you or [NAME].

1    2    3    4    5

l. Is effective in preventing pregnancy.

1    2    3    4    5

m. It is inexpensive.

1    2    3    4    5

n. It is easy to use.

1    2    3    4    5

o. It is a method you can control.

1    2    3    4    5

p. It is a method your partner likes.

1    2    3    4    5

9.2 Next we are going to ask some questions about how confident you are using a condom. Use this scale for your answers:

- 1 Not at all confident
- 2 Slightly confident
- 3 Moderately confident
- 4 Very confident
- 5 Extremely confident

a. How confident are you that you could suggest using a condom even if you were afraid that your partner would reject you?  
1    2    3    4    5

b. How confident are you that you could suggest using a condom even if you were unsure of how your partner felt about condoms?  
1    2    3    4    5

c. How confident are you that you could suggest using a condom even if you were afraid that your partner would think that you have had sex with another person before?  
1    2    3    4    5

d. How confident are you that you could suggest using a condom even if you were afraid that your partner would think you have an STD?  
1    2    3    4    5

e. How confident do you feel in your ability to discuss using condoms with your partner?  
1    2    3    4    5

f. How confident do you feel in your ability to use a condom correctly?  
1    2    3    4    5

g. How confident do you feel in your ability to put a condom on without breaking the sexual mood with your partner?  
1    2    3    4    5

h. How confident do you feel in your ability to buy condoms without feeling embarrassed?  
1    2    3    4    5

i. How confident are you that you could remember to carry a condom with you in case you need one?  
1    2    3    4    5

j. How confident do you feel in your ability to use a condom with your partner even after drinking?  
1    2    3    4    5

k. How confident do you feel in your ability to use a condom with your partner even if you are high?  
1    2    3    4    5

l. How confident do you feel in your ability to use a condom with your partner even if you are sexually excited?  
1    2    3    4    5

**Good job! You are doing great so far! Please continue answering the questions.**

9.3 The next questions ask about how sure you are that you could say NO to sex, alcohol, drugs, etc.-even if you have NEVER done any of these things before. (Choose one answer for each question)

a. How sure are you that you would be able to say NO to having sex with someone you have known for a few days or less?

- i. I Definitely Can Say No
- ii. I Can Say No
- iii. I Don't Know
- iv. I Can't Say No
- v. I Definitely Can't Say No
- vi. Refuse to Answer

b. How sure are you that you would be able to say NO to having sex with someone you want to date again?

- i. I Definitely Can Say No
- ii. I Can Say No
- iii. I Don't Know
- iv. I Can't Say No
- v. I Definitely Can't Say No
- vi. Refuse to Answer

c. How sure are you that you would be able to say NO to having sex with someone who you want to fall in love with you?

- i. I Definitely Can Say No
- ii. I Can Say No
- iii. I Don't Know
- iv. I Can't Say No
- v. I Definitely Can't Say No
- vi. Refuse to Answer

d. How sure are you that you would be able to say NO to having sex with someone who is pressuring you to have sex?

- i. I Definitely Can Say No
- ii. I Can Say No
- iii. I Don't Know
- iv. I Can't Say No
- v. I Definitely Can't Say No
- vi. Refuse to Answer

e. How sure are you that you would be able to say NO to having sex with someone after one or both of you have been drinking alcohol, smoking pot, and/or using drugs, etc.?

- i. I Definitely Can Say No
- ii. I Can Say No
- iii. I Don't Know
- iv. I Can't Say No
- v. I Definitely Can't Say No
- vi. Refuse to Answer

f. How sure are you that you would be able to say NO to having sex with someone who refuses to wear a condom?

- i. I Definitely Can Say No
- ii. I Can Say No
- iii. I Don't Know
- iv. I Can't Say No
- v. I Definitely Can't Say No
- vi. Refuse to Answer

g. How sure are you that you would be able to say NO to having sex with someone who you have had sex with before?

- i. I Definitely Can Say No
- ii. I Can Say No
- iii. I Don't Know
- iv. I Can't Say No
- v. I Definitely Can't Say No
- vi. Refuse to Answer

## SECTION 10: HEALTHY RELATIONSHIPS CHARACTERISTICS (other variables)

Think about a current close relationship (other than with a family member)-it could be a romantic relationship, a close friend, or another. (If you don't have a relationship like that right now, think about one you had in the past, or think about a relationship that you would like to have in the future.)

10.1 Are the following signs of a healthy relationship? (Choose one answer for each question)

- a. One partner acts jealous or possessive.
  - i. Yes
  - ii. No
  - iii. Don't Know
  - iv. Refuse to Answer
- b. One partner criticizes or puts the other one down.
  - i. Yes
  - ii. No
  - iii. Don't Know
  - iv. Refuse to Answer
- c. One of you threatens to hurt themselves or the other person if the relationship ever ends.
  - i. Yes
  - ii. No
  - iii. Don't Know
  - iv. Refuse to Answer
- d. You and your partner feel free to ask honestly for what you want.
  - i. Yes
  - ii. No
  - iii. Don't Know
  - iv. Refuse to Answer
- e. Your partner tries to change or control you (what you do and where you go).
  - i. Yes
  - ii. No
  - iii. Don't Know
  - iv. Refuse to Answer
- f. You and your partner are both comfortable with how physical the relationship is (or isn't).
  - i. Yes
  - ii. No
  - iii. Don't Know
  - iv. Refuse to Answer
- g. You bring out the best qualities in each other.
  - i. Yes
  - ii. No
  - iii. Don't Know
  - iv. Refuse to Answer
- h. You both feel close to each other (not just physically) and are willing to trust each other with personal stuff.

- i. Yes
- ii. No
- iii. Don't Know
- iv. Refuse to Answer

i. You make decisions jointly, with input from each partner.

- i. Yes
- ii. No
- iii. Don't Know
- iv. Refuse to Answer

j. Your partner thinks there are some situations in which it is OK for him or her to hit you.

- i. Yes
- ii. No
- iii. Don't Know
- iv. Refuse to Answer

## SECTION 11: LIFE EVENTS (other variables)

11.1 Life Events are the next set of questions. For each life event, answer "No" if the event did *not* happen to you in the past year, or "Yes" if the life event *did* happen to you in the 12.5.5!\_year.

	No	Yes
1. Has a family member called you names, insulted you, or shamed you on a regular basis?	0	1
2. Was your partner very jealous of you a lot of the time?	0	1
3. Was your partner stingy toward you a lot of the time?	0	1
4. Have you lived with someone who spent a lot of money gambling?	0	1
5. Has a member of your partner's family called you names, insulted you, or shamed you on a regular basis?	0	1
6. Have you wanted to work but could not find a job or lost a job?	0	1
7. Has your partner wanted to work but could not find a job or lost a job?	0	1
8. Have you worried about getting kicked out of school, or what your parents would say about your school performance?	0	1
9. Have you worried about doing poorly in sports?	0	1
10. Were you or a close family member threatened or hurt by gang violence?	0	1
11. Have people gossiped or spread rumors about you?	0	1
12. Has someone important to you attempted suicide and survived?	0	1
13. Has someone important to you committed suicide?	0	1
14. Have you had a serious argument with a friend or friends?	0	1
15. Have you broken up with your partner?	0	1
16. Have you gotten in a car wreck in which someone was hurt or killed?	0	1
17. Has a relative taken over the care of your child (or children)?	0	1
18. Have you lost custody of your child (or children)?	0	1
19. Were you unable to find good child care for your child (or children)?	0	1
20. Has someone important to you died from causes other than suicide?	0	1
21. Have you or someone important to you had an alcohol or drug problem?	0	1
22. Have you or someone important to you gone to an alcohol or drug treatment program?	0	1
23. Have you or someone important to you "fallen off the wagon"?	0	1
24. Have you or someone important to you had a serious health problem: or injury or was hospitalized (not including alcohol or drug problems or treatment)?	0	1

## SECTION 11: FEELINGS AND EMOTIONS (other variables)

You are almost done with the survey. These are the last questions.

11.1 Please mark which best describes how you felt during the past week.

- a. I felt that I could not shake off the blues even with help from my family or friends.
  - i. None of the time (0 days)
  - ii. Rarely or a little of the time (1-2 days)
  - iii. Some of the time (3-4 days)
  - iv. Most or all of the time (5-7 days)
- b. I felt depressed.
  - i. None of the time (0 days)
  - ii. Rarely or a little of the time (1-2 days)
  - iii. Some of the time (3-4 days)
  - iv. Most or all of the time (5-7 days)
- c. I thought my life had been a failure.
  - i. None of the time (0 days)
  - ii. Rarely or a little of the time (1-2 days)
  - iii. Some of the time (3-4 days)
  - iv. Most or all of the time (5-7 days)
- d. I felt fearful.
  - i. None of the time (0 days)
  - ii. Rarely or a little of the time (1-2 days)
  - iii. Some of the time (3-4 days)
  - iv. Most or all of the time (5-7 days)
- e. I felt lonely.
  - i. None of the time (0 days)
  - ii. Rarely or a little of the time (1-2 days)
  - iii. Some of the time (3-4 days)
  - iv. Most or all of the time (5-7 days)
- f. I had crying spells.
  - i. None of the time (0 days)
  - ii. Rarely or a little of the time (1-2 days)
  - iii. Some of the time (3-4 days)
  - iv. Most or all of the time (5-7 days)
- g. I felt sad.
  - i. None of the time (0 days)
  - ii. Rarely or a little of the time (1-2 days)
  - iii. Some of the time (3-4 days)
  - iv. Most or all of the time (5-7 days)
- h. I felt crabby.
  - i. None of the time (0 days)
  - ii. Rarely or a little of the time (1-2 days)
  - iii. Some of the time (3-4 days)
  - iv. Most or all of the time (5-7 days)
- i. I felt hopeless.
  - i. None of the time (0 days)
  - ii. Rarely or a little of the time (1-2 days)

- iii. Some of the time (3-4 days)
- iv. Most or all of the time (5-7 days)

j. I felt like no one cared.

- i. None of the time (0 days)
- ii. Rarely or a little of the time (1-2 days)
- iii. Some of the time (3-4 days)
- iv. Most or all of the time (5-7 days)

k. I felt discouraged.

- i. None of the time (0 days)
- ii. Rarely or a little of the time (1-2 days)
- iii. Some of the time (3-4 days)
- iv. Most or all of the time (5-7 days)

11.2. During the past week ....

- a. Have you often worried that you have made a fool of yourself in front of other people?
  - i. No
  - ii. Yes
- b. Have you often worried that you have made a mistake or done something the wrong way?
  - i. No
  - ii. Yes
- c. Have you been almost always worried about something?
  - i. No
  - ii. Yes
- d. Have you been very worried about whether other people like you?
  - i. No
  - ii. Yes
- e. Have you often gotten worried or nervous?
  - i. No
  - ii. Yes

YOU ARE FINISHED WITH THE SURVEY! THANK YOU VERY MUCH FOR TAKING THE TIME TO COMPLETE THE SURVEY. PLEASE REMEMBER THAT NONE OF YOUR RESPONSES WILL BE ASSOCIATED WITH YOUR NAME. IF YOU HAVE ANY QUESTIONS ABOUT THIS SURVEY PLEASE ASK US.

***"NenUnkUmbi/EdaHiYedo" (We Are Here Now)***

***PARENT SURVEY***

We want to learn more about how you discuss sex with your child and what kinds of topics you discuss. We will be asking you a series of questions about how you talk to your child about sex and how you experience this communication. We thank you for your time.

**SECTION 1: DEMOGRAPHICS**

We would like to start by asking you some questions about yourself.

1. How old are you? \_\_\_\_\_
2. What is the highest grade you have completed? \_\_\_\_\_
3. What is your occupation? \_\_\_\_\_
4. What is your marital status? Please circle one.  
a. married      b. single      c. living with a boyfriend/girlfriend

**SECTION 2: COMMUN/CATION WITH CHILD**

Next we are going to ask some questions about how you feel about your ability to talk to your child about sex and what kinds of things about sex you specifically talk about.

1. How would you rate your ability to communicate with your child in general?
  - a. Difficult
  - b. Somewhat Difficult
  - c. Neither Difficult or Easy
  - d. Somewhat Easy
  - e. Easy
2. How would you rate your ability to communicate with your child about sex?
  - a. Difficult
  - b. Somewhat Difficult
  - c. Neither Difficult or Easy
  - d. Somewhat Easy
  - e. Easy
3. I would like to talk more often with my child about sex and sexuality.
  - a. Yes
  - b. No

4. Have you ever talked with your child about each of the following topics?	YES	NO	I DON'T KNOW
a. What qualities are important in choosing close friends			
b. What qualities to look for in a boyfriend/girlfriend/life partner			

c. How to ask someone out on a date		
d. How boys' bodies change physically as they grow up		
e. How girls' bodies change physically as they grow up		
f. How women get pregnant and have babies		
g. Symptoms of sexually transmitted infections (STIs)		
h. Reasons why people like to have sex		
i. How well birth control can prevent pregnancy		
j. How to choose a method of birth control		
k. How to say no if someone wants to have sex and you don't want to		
l. How well condoms can prevent sexually transmitted infections (STIs)		
m. Menstruation (having menstrual periods)		
n. The importance of not pressuring other people to have sex		
o. How your child will make decisions about whether or not to have sex		
p. Consequences of getting pregnant/getting someone pregnant		
q. How to use a condom		
r. Reasons why your child should not have sex at this time		
s. Masturbation		
t. What it feels like to have sex		
u. Homosexuality/people being gay		
v. Wet dreams [measured for parents of boys only]		
w. What to do if a partner doesn't want to use a condom		
x. How people can prevent getting sexually transmitted infections (STIs)		
V. How your child will know if he/she is in love		

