### **6.3.2. List of Data Source Materials and Measures (Table 2 below).**

**Student Survey:** To assess students' participation in N/E, we draw from several existing measurements that have been implemented and validated in research studies with AI youth. Primary outcome measure: Condom use will measure frequency of condom use relative to frequency of sex during sexual intercourse using questions derived from the Risk Behavior Assessment. Secondary outcome measures: These will include the number of sex partners; age of onset of sexual intercourse; frequency of sexual intercourse; pregnancy history; frequency and type of birth control used during sexual intercourse relative to the frequency of sexual intercourse; and frequency and types of substance use (cigarettes, marijuana, alcohol, and methamphetamine). Tertiary outcome measures: Parent/legal guardian communication is measured by the frequency and types of SRH topics that parent/legal guardian and child discussed. Cultural identity is measured using two established measurements: One measure assesses the extent to which a student identifies with his or her American Indian culture and feels cultural pride, and the other measure assesses frequency and type of participation in cultural activities. Access to SRH services is measured by frequency and type of SRH service used (ever been tested for STIs and follow-up, ever been tested for HIV and follow-up, ever been tested for HCV and follow-up, ever been pregnant/gotten someone pregnant and follow-up). Other variables to be measured in N/E that assess attitudes, intentions, skills, and mental health are: Motivation to avoid STIs, HIV, HCV, and pregnancy, as measured by asking students how important it is to them to keep themselves (or someone else) from getting an STI, HIV, and HCV, and how important it is to them to keep from getting pregnant or getting someone pregnant. Intention to use condoms and/or birth control is measured by asking students how likely it is they will use condoms and/or birth control the next time they have sexual intercourse. Intention to abstain from sex is measured by asking students how likely it is that they will not participate in sexual intercourse. Condom and birth control use self-efficacy is measured by assessing confidence in one's ability to use condoms and birth control. Refusal skills regarding sex are assessed by how strongly students believe they can say no to sex. Knowledge about STIs, HIV, HCV, pregnancy, and healthy relationship characteristics are measured using true/false/don't know questions. Mental health is assessed using two established measures: One measure assesses depression using the C-ESD, and the other measurement assesses exposures to stressful life events by assessing lifetime occurrences of a series of negative events. Standard demographic measures in the student survey are age, gender, sexual orientation, school, and highest grade completed.

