
**Parent/Legal Guardian Survey.** The parent/legal guardian survey is based on parents'/legal guardians' participation in Native Voices. It includes a list of SRH topics about which the parent/legal guardian has spoken to the child and the frequency of times discussed. The parent/legal guardian measures have been validated in previous studies evaluating parent/child SRH communication and have been used by [name] in her Greenland studies. The SRH topic list and frequency is the same as in the student survey, only adapted for parents/legal guardians. Standard demographic measures included in the parent/legal guardian survey are age, gender, marital status, highest grade completed, and occupation.

**Barriers/Facilitators Discussion Guide.** The barriers/facilitators discussion guide is a qualitative assessment using open-ended questions that address the factors impeding and facilitating SRH services for AI youth on the Fort Peck Reservation. The guide is based on the 8 service domains for evidence-based clinical practices outlined in the CDC's Contraceptive and Reproductive Health Services for Teens: Evidence-based Clinical Best Practices Guide(80-82)-namely, contraceptive access; provision of hormonal contraception/IUD; emergency contraception; cervical cancer screening; STI/HIV/HCV testing and treatment; cost, confidentiality, consent; health center infrastructure; and health center environment.

**Coordination and Implementation Monitoring Plan Tracking Log.** The tracking log will monitor the progress toward completion of the 8 SRH service domains identified from the barriers/facilitators discussion

guide and corresponding evidence-based clinical practice elements.

**Focus Groups.** Data collection related to Aim 3 of our study, which is to evaluate the fidelity and acceptability of N/E, includes a focus group guide, as described above. The Aim 3 focus groups will include questions such as what experiences/activities they liked and/or did not like about the intervention, what educational information they did and/or did not like about the intervention, and what recommendations they have for improving the intervention.

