**Table 2. NIE Measures.**

**Table 2. N/E Measures.**

Data Collection Instruments and Measures	Data Collection: Baseline & Months				Description of Measures Number of Items; Scale Anchors; Benchmark Values	
	Base	3	9	12		
Student Survey						
Primary Outcome Variable						
Proportion of condom use during sexual intercourse (SI)	X	X	X	X	2 items; number of times condom used relative to number of times had SI	
Secondary Outcome Variables						
Age of onset of sexual intercourse	X	X	X	X	2 items; ever had SI & age at first SI	
Number of sex partners	X	X	X	X	2 items; lifetime & past-month sex partners	
Frequency of sexual intercourse	X	X	X	X	1 item; frequency of SI in past month	
Pregnancy history	X	X	X	X	1 item; number of pregnancies	
Type & frequency of birth control (BC) during sexual intercourse	X	X	X	X	3 items; type of BC use and number of times BC used during SI	
Type & frequency of substance use (SU) during sexual intercourse	X	X	X	X	1 item measures SU with SI; 5 items measure lifetime and past month SU	
Tertiary Outcome Variables						
Type & frequency of parent/legal guardian-child SRH communication	X	X	X	X	24 items Likert scale; higher score = higher communication	
Cultural identity & participation in cultural activities	X	X	X	X	3 items cultural identity ( $\alpha = .75$ ); 2 items cultural activities engagement ( $\alpha = .46$ )	
Type & frequency of SRH services	X	X	X	X	9 items; frequency, type, and follow-up of SRH services used	
Other Variables						
Motivation to avoid STIs, HIV, HCV, & pregnancy	X	X	X	X	Up to 9 items; 1 (very true) to 5 (very untrue); 1 = more positive attitude/motivation	
Condom & birth control use intention & self-efficacy	X	X	X	X	4 items per intention; 1 (very true) to 5 (very untrue); 1 = higher intention; 6 self-efficacy items; 1 (very easy) to 4 (very hard); 1 = high self-efficacy	
Abstinence	X	X	X	X	3 items; 1 (strongly disagree) to 4 (strongly agree); 4 = more supportive of teen abstinence	
Refusal skills regarding sex	X	X	X	X	7 items; 1 (I definitely can say no) to 5 (I definitely can't); 1 = stronger refusal skills	
Knowledge of STIs, HIV, HCV, pregnancy, & health relationships	X	X	X	X	Range of 4 to 10 items per topic; True/False/DK; Average proportion of questions correct	
Depression (CES-D) & exposure to stressful life events	X	X	X	X	CES-D — 7 items ( $\alpha = .80$ ); Life Events — 24 items; Yes/No; number of events observed	
Student Demographics						

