H1: AI youth who participate in N/E will demonstrate increased condom use at 3, 9, and 12 months. (12 months will be used in the Primary Outcome analysis; 3 and 9 months will be used in the Secondary Outcomes analysis.) H2: AI youth who participate in N/E will demonstrate increased use of other birth control at 3, 9, and 12 months. They also will demonstrate a decrease in sexual risk behaviors as measured by reduced number of sex partners, delayed onset of sexual intercourse, and decreased substance use during sex, at 3, 9, and 12 months. (Secondary Outcomes) H3: N/E parents/legal guardians and youth will demonstrate significantly increased communication about topics related to SRH at 3, 9, and 12 months. AI youth who participate in the cultural mentoring program will demonstrate significantly increased understanding of cultural values related to traditional AI beliefs regarding SRH at 3, 9, and 12 months. And AI youth who participate in N/E will report significantly increased use of SRH services at 3, 9, and 12 months as a result of improved coordination among education, health care, and social service agencies on the Fort Peck Reservation. (Tertiary Outcomes) AIM 3: Evaluate the fidelity and acceptability of N/E. N/E's fidelity and acceptability will be evaluated using qualitative methods, including focus groups, activity logs, and staff field notes and meetings.

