### **SECTION 3: COMMUNICATION ABOUT SEX WITH PARENTS/LEGAL GUARDIAN** (*tertiary outcome variable*)

Now you are going to be asked questions about what kinds of topics related to sex you do or do not talk with your parents/legal guardian about.

3.1. Have you talked with your parent/legal guardian about each of the following topics in the past year?

	.	YES	NO	I DON'T KNOW
a. What qualities are important in choosing close friends				
b. What qualities to look for in a boyfriend/girlfriend/life partner				
c. How boys' bodies change physically as they grow up				
d. How girls' bodies change physically as they grow up				
e. How women get pregnant and have babies				
f. Symptoms of sexually transmitted infections (STIs)				
g. Reasons why people like to have sex				

h. How well birth control can prevent pregnancy			
i. How to choose a method of birth control			
j. How to say no if someone wants to have sex and you don't want to			
k. How well condoms can prevent sexually transmitted infections (STIs)			
l. Menstruation (having menstrual periods)			
m. The importance of not pressuring other people to have sex			
n. How you will make decisions about whether or not to have sex			
o. Consequences of getting pregnant/getting someone pregnant			
p. How to use a condom			
q. Reasons why you should not have sex			
r. Masturbation			
s. What it feels like to have sex			
t. Homosexuality/people being gay			
u. Wet dreams measured for boys only			
v. What to do if a partner doesn't want to use a condom			
w. How people can prevent getting sexually transmitted infections (STIs)			
x. How you will know if you are in love			

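### Parent–child communication (tertiary, H3) is planned as one 24-topic frequency scale for both informants, but parents are asked 'ever' and students 'past year', with no frequency

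*Combined protocol and SAP*

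**What the plan says.** **Planned measure.** Section 6.3.2 defines the student outcome this way: "Parent/legal guardian communication is measured by the frequency and types of SRH topics". For the parent survey it states: "The SRH topic list and frequency is the same as in the student survey". Table 2 gives both informants the same entry, "24 items Likert scale; higher score = higher communication", in rows labelled as type and frequency. The registry printout (Other Pre-specified Outcome Measures) repeats the 24-item Likert description.

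**Instruments in the appendix.**
- Parent Survey, Section 2, item 4, asks whether the parent has ever "talked with your child about each of the following topics". It lists 25 topics.
- Student survey, Section 3, item 3.1: "Have you talked with your parent/legal guardian about each of the following topics in the past year". It lists 24 topics.

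Both lists are answered yes, no or don't know.

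**Hypothesis and timing.** H3 in the registry printout reads: "N/E parents/legal guardians and youth will demonstrate significantly increased communication about topics related to SRH at 3, 9, and 12 months". Students are surveyed at baseline, 3, 9 and 12 months, and parents at baseline, 9 and 12 months only (Sections 2.3.2 and 4.1, Table 2). The GLMM part of Section 3 models the tertiary outcomes as continuous responses, with a fixed effect of time and a random effect for school.

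**The concern.** The protocol describes one instrument and the appendix holds two others, which differ from it in response scale and recall period; the parent list also differs in length. The parent item matters most because it is cumulative. Once a topic has been discussed, a truthful answer stays yes for good, and further conversation about it leaves no trace. Increasing that conversation is what the family sessions are for, so the item misses part of the intended effect and picks up ordinary accrual as teenagers grow older.

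The student item does not have that defect. However, its one-year window reaches back before the intervention at the early follow-up, which dilutes any contrast with baseline.

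At stake is the interpretation of one tertiary outcome. The primary condom-use analysis is unaffected.

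**Working it through.** The plan gives no power or precision figure for this outcome, so there is none to reproduce. The checks are a comparison of the instruments, the recall arithmetic and an illustration of accrual.

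**1. Instruments against plan**

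| | Plan (6.3.2, Table 2) | Parent survey | Student survey |
|---|---|---|---|
| Topics | 24 | 25 (adds asking someone out on a date) | 24 |
| Response | Likert, frequency | yes / no / don't know | yes / no / don't know |
| Recall | same for both | lifetime | past year |

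One topic on each list is for boys only, so the number of applicable items also varies by sex.

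**2. Student recall window.** The share of a 12-month window that precedes intervention start, at t months, is (12 − t)/12:
- 3 months: 9/12 = 75%
- 9 months: 3/12 = 25%
- 12 months: 0/12 = 0%

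The Wave 1 calendar agrees. With a start on 1 September 2019 (progress report, G.10.c), the share is about 70–75% in December 2019, 24–30% in May/June 2020 and 0% in September 2020. The first family session is undated. If it came 1 to 2 months after the start (assumed) and the clock ran from there, the shares would be 83–92%, 33–42% and 8–17%.

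**3. Parent accrual with no intervention effect.** One-year gain = 25 × (1 − p) × h, where p is the share of topics already discussed at baseline and h is the yearly uptake among the rest. Neither value is in the documents; both are assumed.
- Low (p = 0.70, h = 0.05): 25 × 0.30 × 0.05 = 0.375 topics
- Middle (p = 0.60, h = 0.10): 25 × 0.40 × 0.10 = 1.0 topic
- High (p = 0.50, h = 0.20): 25 × 0.50 × 0.20 = 2.5 topics
- Very low uptake (p = 0.60, h = 0.02): 25 × 0.40 × 0.02 = 0.2 topics

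**4. Would such a gain stand out?** This is a simple before–after comparison, used only for scale.
- Parents followed: 456 × 0.85 ≈ 388, applying the plan's 15% attrition to parents (assumed); 388/5 ≈ 78 per school.
- Design effect: 1 + (77.6 − 1) × 0.016 ≈ 2.23, applying the plan's ICC to the change score (assumed).
- SD of change 2 (assumed): SE = 2/√388 × √2.23 ≈ 0.15.
- SD of change 5 (assumed): SE = 5/√388 × √2.23 ≈ 0.38.

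| Null gain | z, SD 2 | z, SD 5 |
|---|---|---|
| 0.2 | 1.3 | 0.5 |
| 0.375 | 2.5 | 1.0 |
| 1.0 | 6.6 | 2.6 |
| 2.5 | 16.5 | 6.6 |

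**5. Does the time term remove accrual?** Section 2.3.5 gives one baseline for all clusters and then surveys each cluster only once it has begun the intervention. On that reading every parent record after baseline carries intervention = 1. The indicator then equals the sum of the post-baseline period indicators, and categorical period effects cannot be separated from it. Later waves may also wait longer. Section 4.1 puts all parent baselines in Fall 2019, while Wave 3 runs in 2020–2021. Over two years the middle case gives 25 × 0.40 × (1 − 0.90²) = 1.9 topics.

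**The case against.** **The model adjusts for time.** Natural accrual is a time trend, and the planned model has a fixed effect for time. A before–after z is not the planned test. Both statements are true, and the z values above show only scale. The rescue fails on the schedule as written, because there is no untreated follow-up from which to estimate the trend. If so, that weakness affects every outcome. It is used here only to show that the time term is not a safe answer to a cumulative item. The trial-design figure is not shown in the text available and might add survey rounds.

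**Stronger readings a reader might infer.**
- *Student scores mostly describe the period before the intervention.* This holds at 3 months only.
- *Parent scores can only rise.* Recall error or a switch to don't know can lower an observed score, and a parent at yes on every topic cannot rise. Only a consistently answered score is non-decreasing.
- *H3 would be declared significant for parents with no effect.* The table shows that this depends on uptake and SD, neither of which is documented.
- *The mismatch spoils a parent–child comparison.* Section 3 plans no dyadic analysis.

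**Validation and timing.** Section 6.3.2 says the parent measures were validated earlier, so changing them has a real cost. H3 at 3 months can still be tested on student report; only the parent part lacks data. Both points stand. Some appendix pages were removed before review, so another survey version cannot be excluded.

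**Conclusion.** The inconsistency is established by reading the documents: no frequency response on either topic list, two recall periods, and 25 topics against 24. The parent item is cumulative if answered consistently and cannot register more talk on topics already covered, so a rise in that score is not by itself evidence of an intervention effect.

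The size is conditional. Over the assumed ranges for baseline and uptake, the null gain is about 0.4 to 2.5 of 25 topics, which is conspicuous if the SD of change is 2. With 2% uptake and clustering allowed for, it is not significant (z ≈ 1.3). Dilution of the student score is mainly a 3-month problem and is absent at 12 months when counted from intervention start. The outcome is tertiary, but the correction is worth making because it is cheap.

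**What to change.** Put the same 24 topics, the frequency scale planned in Table 2 and one bounded recall period on both surveys. Choose the period to fit both the survey gaps and the family sessions, which Table 1 places every other month. A 3-month window matches the shortest gap, but at 9 months it would miss the first six months of delivery, so the choice should be stated and justified. Score the mean over applicable items and say how don't know is handled. Limit the parent-reported part of H3 to 9 and 12 months.

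The cost is an edit to two REDCap forms, with no extra visits, and some loss of comparability with earlier uses of the list.

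Baseline was scheduled from March 2019 and the file contains approvals dated 2020, so it may already be collected. In that case keep the existing lists for continuity and add the frequency item to the remaining surveys. Correct Table 2 and Section 6.3.2 to match what was asked, and report the parent lifetime score descriptively, not as evidence of effect. A late change has a further cost: the new frequency item would have no baseline value.
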